15.4 Vital Signs

The following treatment labels will be used in tables and listings:

- Screening: During the screening period
- Run-in Period: During run-in period

- Microgynon + Placebo or Microgynon + Cladribine: For each measurement from Day 9 on until Day 14
- Follow-up: During follow-up/end of study period

Vital signs will be listed by subject and time-point and summarized for absolute values and changes-from-baseline by treatment sequence, period, treatment and visit using descriptive statistics. Descriptive statistics tables will start at baseline.

15.5 ECG Evaluation

The following treatment labels will be used in tables and listings:

- Screening: During the screening period
- Microgynon + Placebo or Microgynon + Cladribine: For each measurement on Day 9 and Day 14
- Follow-up: During follow-up/end of study period

ECG data will be summarized for absolute values and changes-from-baseline by treatment sequence, period, treatment, and visit using descriptive statistics. Descriptive statistics tables will start at baseline. Clinically significant ECG findings for individual subjects will be listed and summarized.

The time intervals (PR, QRS, RR, QT and corrected QT intervals [based on Fridericia's formula, QTcF]) will be summarized descriptively by treatment sequence, period, treatment and visit.

The Fridericia's Correction (QTcF) is derived as follows:

Fridericia's Correction (QTcF)
$$QTc_f = \frac{QT}{\sqrt[3]{RR}}$$

where: RR = RR-interval measured in seconds.

Baseline for ECG is defined as Day 9 pre-dose (for each period).

Observed QTcF values will be categorized according to their absolute values into the categories

- \bullet < 430 ms,
- > 430 and < 450 ms.

- $> 450 \text{ and} \le 470 \text{ ms}$,
- $> 470 \text{ and} \le 500 \text{ ms}$, and
- > 500 ms,

and categorized according to their absolute change from baseline into the categories

- \leq 30 ms,
- \bullet > 30 and < 60 ms, and
- \bullet > 60 ms.

The number and percentage of subjects by these categories at any post-dose assessment (post-dose to intake of placebo or cladribine) will be tabulated by treatment sequence, period and treatment.

All ECG measurements will be listed, with investigator reported abnormalities indicated.

Investigator reported interpretation results will also be listed and tabulated by treatment sequence, period and treatment using the number and percentage of subjects for each interpretation category (Normal, Abnormal Not Clinically Significant [NCS], Abnormal Clinically Significant [CS].

16.1 Pharmacokinetics

The following treatment labels will be used in tables and listings:

Run-in Period: During run-in period (for EE and LNG only)

Microgynon + Placebo or Microgynon + Cladribine.

General Specifications for Plasma Concentration Data

PK concentration data will be presented in tables and descriptively summarized by treatment and nominal time point using n, arithmetic mean, SD, median, minimum, maximum, and CV%. Values below the LLOQ will be taken as zero for descriptive statistics of PK concentrations.

Descriptive statistics of PK concentration data will be calculated using values with the same precision as the source data, and rounded for reporting purposes only. The following conventions will be applied when reporting descriptive statistics of PK concentration data:

Mean, Min, Median, Max: 3 significant digits

SD: 4 significant digits

CV%: 1 decimal place

For final evaluations values greater than the upper limit of quantification (ULOQ) are not accepted and should be replaced by valid numeric values from dilution measurement. Missing concentrations (e.g. no sample, insufficient sample volume for analysis, no result or result not valid) will be reported and used generally as "N.R.". Pre-dose samples that occur before the first drug administration will be assigned a time of 0 hours, as if the sample had been taken simultaneously with the study drug administration.

General Specifications for PK Parameter Data

PK parameter data will be descriptively summarized: n, arithmetic mean, SD, median, minimum, maximum, CV%, geometric mean (GeoMean), the geometric coefficient of variation (GeoCV%), and the 95% CI for the GeoMean.

PK parameter C_{max} will be reported with the same precision as the source data. All other PK parameters will be reported to 3 significant figures. In export datasets, as well as in the SDTM PP domain, PK parameters will be provided with full precision, and will not be rounded. Descriptive statistics of PK parameter data will be calculated using full precision values, and rounded for reporting purposes only.

The following conventions will be applied when reporting descriptive statistics of PK parameter data:

Mean, Min, Median, Max, GeoMean, 95% CI: 3 significant digits

SD: 4 significant digits

CV%, GeoCV%: 1 decimal place

Ratio of GeoMean and 90% CI 4 decimal places

All statistical analyses and descriptive summaries of pharmacokinetic data will be performed on the PK Analysis Set. All available concentration/PK data will be listed. Data of subjects not in the PK analysis set or invalid data will be flagged accordingly; a reason for exclusion will be detailed in the CSR (e.g. a footnote or a table of exclusions). Any flags should be included in the study specific ADaM data sets.

16.1.1 Primary Pharmacokinetic Endpoints

The PK evaluation will be based upon the PK Analysis Set. The statistical analysis of primary PK parameters $AUC_{\tau,ss}$ and $C_{max,ss}$ of EE and LNG (the active ingredients of the Microgynon treatment) will be performed using an analysis of variance (ANOVA) model including TREATMENT, PERIOD, SEQUENCE and SUBJECT(SEQUENCE) as fixed effects. Parameters will be log-transformed before they are processed. LSMEANS for Test – Reference differences will be estimated for all 4 primary endpoints together with 90% confidence intervals, resulting in Test/Reference ratios and corresponding 90% confidence intervals following backtransformation.

Bioequivalence (which means absence of drug-drug interaction) will be concluded, if all four 90% CIs for the TEST/REFERENCE ratios are fully contained within the [0.8000 to 1.2500] acceptance range.

Scatter plots will be produced for the individual primary PK parameters by treatment indicating the geometric means within each treatment. Boxplots for primary PK parameters by treatment will also be provided.

16.1.2 Secondary Pharmacokinetic Endpoints

Secondary PK parameters calculated for EE and LNG: $C_{min,ss}$; C_{trough} ; $t_{max,ss}$; $C_{av,ss}$; and peak-to-trough fluctuation (PTF%). Secondary PK parameters calculated for Cladribine: C_{max} and t_{max} .

Secondary parameters will be listed.

Summary statistics will be provided for all secondary PK parameters for EE, LNG and cladribine in plasma by analyte, treatment and day, if applicable.

16.1.3 Plasma Concentration Data

Concentrations of EE, LNG and cladribine will be tabulated and displayed graphically. Summary statistics will be provided by analyte, treatment and nominal timepoint and day.

The following figures will be produced for the EE and LNG plasma concentrations on Day 14:

- Arithmetic mean plasma concentration-time profiles overlaying all treatments on linear and semi-logarithmic scale
- Arithmetic mean plasma concentration-time profiles overlaying all treatments on linear scale including SD error bars
- Individual plasma concentration-time profiles overlaying subjects, for each treatment separately on linear and semi-logarithmic scale
- Individual plasma concentration-time profiles overlaying all treatments, separately for each subject on linear and semi-logarithmic scale

The following figures will be produced for the cladribine plasma concentrations on Days 10, 11, 12 and 13 separately:

- Individual plasma concentration-time profiles on linear and semi-logarithmic scale overlaying subjects, for each treatment separately on linear and semi-logarithmic scale (x-scale: relative actual time related to corresponding cladribine administration)
- Individual plasma concentration-time profiles on linear and semi-logarithmic scale overlaying all treatments, separately for each subjects on linear and semi-logarithmic scale (x-scale: relative actual time related to corresponding cladribine administration)

The following figures will be produced for the cladribine plasma concentrations overlaying Days 10, 11, 12 and 13:

- Individual plasma concentration-time profiles on linear and semi-logarithmic scale separately for each treatment and subjects on linear and semi-logarithmic scale (x-scale: relative actual time related to corresponding cladribine administration)
- Arithmetic mean plasma concentration-time profiles for each treatment separately on linear and semi-logarithmic scale
- Arithmetic mean plasma concentration-time profiles for each treatment separately on linear scale including error bars

The following listing will be produced:

• Plasma concentrations will be listed for each analyte by treatment, subject, and nominal time and day. Excluded plasma concentrations will be flagged.

Document No.

Object No.

CONFIDENTIAL
INFORMATION

16.1.4 Estimation of Individual Pharmacokinetic Parameters

The computer program Phoenix® WinNonlin® version 6.4, or higher (Certara, L.P., [name]) will be used to derive PK parameters applying Noncompartmental analysis (NCA). The statistical software SAS® (Statistical Analysis System, SAS-Institute, Cary NC, USA, windows version 9.1 or higher) may be used to generate additional PK parameters, produce tables, listings and figures.

The following PK parameters will be calculated for Day 14, when appropriate:

Table 2 PK Parameters of EE and LNG

Symbol	Definition
C _{max,ss}	Maximum observed concentration in steady state
C _{min,ss}	Minimum observed concentration in steady state during a complete dosing interval (τ)
Ctrough	Measured concentration at the end of a dosing interval at steady state (taken directly before next administration)
t _{max,ss}	Time to reach the observed maximum (peak) concentration at steady state
$AUC_{\tau,ss}$	Area under the plasma concentration-time curve in steady state during a complete dosing interval (τ)
Cav,ss	Average plasma concentration at steady state during a complete dosing interval (τ); $C_{av,ss}$ = $AUC_{\tau,ss}$ / τ
PTF %	Peak-to-trough fluctuation over 1 complete dosing interval at steady state

The following PK parameters will be calculated for Days 9, 10, 11, 12 and 13, when appropriate:

Table 3 PK Parameters of cladribine^a

Parameter	Full description
C_{max}	Maximum observed concentration (Days 10-13 only)
t _{max}	Time to reach the observed maximum (peak) concentration (Days 10-13 only)
C _{pre}	Measured concentration during repeat-dosing taken directly before drug administration (on Day 10-13).

a A steady-state will not be achieved with once daily dosing of cladribine, therefore single-dose PK parameters are given. The PK sampling of cladribine only serves the purpose to proof regular exposure to cladribine.

Individual PK parameters will be calculated using actual elapsed time since dosing, given with a precision of 14 significant digits or the SAS format Best12. The pre-dose sample will be considered as if it had been taken simultaneously with the administration of study drug. In cases where the actual sampling time is missing, calculations will be performed using the scheduled time. Otherwise, there will be no further imputation of missing data.

Samples that are collected outside the specified time windows specified in the CTP will be included in the PK parameter estimation (NCA) but will be excluded from the concentration summary and mean concentration plots.

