8.5 Pharmacokinetics

Whole blood samples of approximately 5 mL will be collected for measurement of plasma concentrations of EE and LNG, as specified in the [SoA](#) (see [Section 1.3](#)). A maximum of 4 samples may be collected at additional time points during the study if warranted and agreed upon between the Investigator and the Sponsor. The actual date and time (24-hour clock time) of each sample will be recorded.

Whole blood samples of approximately 3 mL will be collected for measurement of plasma cladribine, as specified in the [SoA](#) (see [Section 1.3](#)). A maximum of 4 samples may be collected at additional time points during the study if warranted and agreed upon between the Investigator and the Sponsor. The actual date and time (24-hour clock time) of each sample will be recorded.

The quantification of EE, LNG and cladribine in plasma will be performed using a validated bioanalytical method. Concentrations will be used to evaluate the PK of EE, LNG and cladribine.

Remaining samples collected for analyses of EE, LNG and cladribine concentration may also be used to evaluate safety or efficacy aspects related to concerns arising during or after the study.

Details on process for collection and shipment of these samples are in a separate Lab Manual provided by [PPD](#). Retention time and possible analyses of samples after the end of study are specified in the respective ICF.

Drug concentration information that would unblind the study will not be reported to investigative sites or blinded personnel.

Full details of the bioanalytical methods used will be described in a separate bioanalytical protocol. Venous blood samples will be collected as listed in the Schedule of Assessments (see [Section 1.3](#)).

- In the Run-in-Period, plasma samples for PK analysis of EE and LNG will be collected on Days 7, 14, and 21. In Study Periods 1 and 2 plasma samples for PK analysis of EE and LNG will be collected on Day 13 in the morning predose of Microgynon administration, and on Day 14 predose (with respect to Microgynon) and at 0.5, 1, 2, 4, 6, 8, 12, and 24 hours (Day 15) postdose.

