- Plasma samples for PK analysis of cladribine will be collected as follows: A predose sample in the morning of Day 9 before first cladribine/placebo administration; predose samples (= through samples) and postdose samples on Days 10, 11, 12, and 13 at the following times: predose, 0.25, 0.5, 1.0, 1.5, 2.0 hours postdose. These determinations serve the purpose to ensure appropriate exposure to study drug, and not to determine PK endpoints.

The exact date/time of sample collection should be recorded in the eCRF. The accepted time deviations from planned PK sampling times are listed in the table below:

Table 4 Accepted Time Deviations From Planned PK Sampling Times

Time Point (Relative Time)	Window Allowance
Predose	- 60 min to - 1 min
0.25 – 1 h postdose	± 2 min
> 1 h – 12 h postdose	± 5 min
> 12 h – 48 h postdose	± 10 min

h=hour; min=minutes.

Pharmacokinetic calculations will be performed using commercial software such as PPD

Other parameters may be added as appropriate. Final PK parameters reported will be detailed in the statistical analysis plan.

Pharmacokinetic analysis will use actual dates and times as recorded on the eCRF. Other data handling procedures will be detailed in the statistical analysis plan.

The following PK parameters will be calculated, when appropriate:

Table 5 PK Parameters of EE and LNG

Symbol	Definition
$C_{max,ss}$	Maximum observed concentration in steady state
$C_{min,ss}$	Minimum observed concentration in steady state during a complete dosing interval (τ)
C_{trough}	Measured concentration at the end of a dosing interval at steady state (taken directly before next administration)
$t_{max,ss}$	Time to reach the observed maximum (peak) concentration at steady state
$AUC_{\tau,ss}$	Area under the plasma concentration-time curve in steady state during a complete dosing interval (τ)
$AUC_{\tau,ss} / \tau$	Average plasma concentration at steady state during a complete dosing interval (τ)
PTF %	Peak-to-trough fluctuation over 1 complete dosing interval at steady state

Table 6 PK Parameters of Cladribine^a

Parameter	Full description
C _{max}	Maximum observed concentration
t _{max}	Time to reach the observed maximum (peak) concentration
C _{pre}	Measured concentration at the end of a dosing interval during repeat-dosing (taken directly before next administration)

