Appendix 6 Pharmacokinetic Parameters

Symbol	Definition
AUC_{τ}	The area under the concentration-time curve (AUC) over the dosing interval from $T_1=0$ hours to $T_2=\tau$ h. Calculated using the mixed log linear trapezoidal rule (linear up, log down). For single dose, AUC_{τ} is calculated as a partial area with the defined time range. In multiple dose profiles AUC_{τ} is calculated at steady state from 1 predose time point to the dosing interval time. In cases where the actual observation time is not equal to the scheduled observation time AUC_{τ} will be calculated based on the estimated concentration at τ hours, and not the concentration at the actual observation time.
C_{av}	The average concentration at steady state. $C_{av} = AUC_{\tau} / \tau$.
C_{pre}	Measured concentration at the end of a dosing interval during repeat-dosing (taken directly before next administration)
C_{max}	Maximum observed concentration
C_{min}	The minimum observed concentration during a complete dosing interval
C_{trough}	The concentration observed immediately before next dosing (corresponding to predose or trough concentration for multiple dosing)
PTF%	The peak trough fluctuation within a complete dosing interval at steady state. $PTF = 100 * (C_{max} - C_{min}) / C_{av}$.
t_{max}	The time to reach the maximum observed concentration collected during a dosing interval (unless otherwise defined, take the first occurrence in case of multiple/identical C_{max} values)
t_{min}	The time to reach the minimum observed concentration collected during a dosing interval
τ	Dosing interval

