8.1 Definition of Protocol Deviations and Analysis Sets

Important protocol deviations are protocol deviations that might significantly affect the completeness, accuracy, and/or reliability of the study data or that might significantly affect a subject's rights, safety, or well-being.

The following deviations will be identified and confirmed prior to or at the Data Review Meeting at the latest.

Important protocol deviations include but are not limited to

- Deviations from the inclusion and exclusion criteria
- Concomitant medication violations (see Section 6.5.2 of the protocol)
- Use of prohibited medicines (see Section 6.5.3 of the protocol)
- Subjects that receive incorrect treatment or dose
- Sample processing errors that may lead to inaccurate bioanalytical results
- Deviation from Good Clinical Practice
- Non-compliance to study procedures or deviations from study procedures likely to affect the primary endpoints (e.g. subject develops withdrawal criteria whilst on the study but is not withdrawn)

In addition, for the definition of the PK analysis set (see section 8.2) events likely to affect the comparability between treatments of PK results will be identified. Important events to be considered are:

- Vomiting or diarrhea following oral dosing (these instances will be discussed on a caseby-case basis)
- Deviation from study medication compliance in terms of medical conditions and/or AEs that may have interfered with drug disposition or with respect to factors likely to affect the primary endpoints

All important protocol deviations will be documented in Clinical Data Interchange standard consortium (CDISC) Study Data Tabulation Model (SDTM) dataset whether identified through sites monitoring, medical review or programming.

In addition, pre-dose/trough samples which have been taken after the subsequent dosing will be reported as protocol deviation. The resulting concentrations will be included in concentration listings but excluded from descriptive statistics of trough concentrations.

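### A 24-h EE/LNG sample drawn after the Day 15 Microgynon tablet is barred from trough summaries but stays in the NCA, where it inflates AUCtau,ss

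*SAP*

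**What the plan says.** Protocol 8.5 schedules the EE and LNG profile "on Day 14 predose (with respect to Microgynon) and at 0.5, 1, 2, 4, 6, 8, 12, and 24 hours (Day 15) postdose". Table 4 in the same section gives pre-dose samples a window of 60 to 1 min before dosing. The 24-h sample falls in the row "> 12 h – 48 h postdose", which allows ±10 min around nominal time and does not refer to the Day 15 tablet.

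Two SAP rules deal with samples that go wrong:

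- SAP 8.1: "pre-dose/trough samples which have been taken after the subsequent dosing will be reported as protocol deviation". Their concentrations are "included in concentration listings but excluded from descriptive statistics of trough concentrations". The non-compartmental analysis (NCA) is not mentioned.
- SAP 16.1.4: "Samples that are collected outside the specified time windows specified in the CTP will be included in the PK parameter estimation (NCA". They are dropped only from the concentration summaries and mean plots.

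SAP 16.1.4 also says of time zero: "The pre-dose sample will be considered as if it had been taken simultaneously with the administration of study drug". Other samples use actual elapsed time, and beyond substituting scheduled times for missing ones nothing further is imputed. Protocol Appendix 6 says that, when the observation time is off schedule, AUCtau "will be calculated based on the estimated concentration at" tau. It prescribes linear-up/log-down trapezoids but no method for that estimate.

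**The concern.** SAP 8.1 recognises that a trough drawn after the next dose is not a trough, and acts on this for descriptive statistics. The same concentration is not kept out of the parameter calculation, where it does more harm. The 24-h value closes the 12–24 h segment, which is half of the dosing interval. If it comes from the next absorption phase, AUCtau,ss is too high for that participant and period. Cav,ss rises in proportion, and PTF% falls because Cav,ss is its denominator.

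AUCtau,ss of EE and of LNG are two of the four primary endpoints (SAP 16.1.1). An error in one period enters that participant's Test/Reference difference directly and adds residual variance to the 90% CI.

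A late draw is not the only route. A 24-h sample can be within ±10 min of nominal and still follow the tablet, if the Day 15 tablet was taken on time or slightly early. Such a sample is in window and enters the NCA without needing the sentence in 16.1.4 at all.

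**Working it through.** The documents give no figure to reproduce on this point, so the check is numerical.

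**Inputs from the documents.** Sampling at 0, 0.5, 1, 2, 4, 6, 8, 12 and 24 h; tau = 24 h; linear-up/log-down AUC (Appendix 6); 16 evaluable participants (Protocol 7.2); acceptance range 0.80 to 1.25 (SAP 16.1.1).

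**Assumptions, not in the documents.** One-compartment oral model at steady state, half-life 12–24 h, ka 1–2 per h, next tablet at exactly 24 h, sample drawn x hours later, and concentration at 24 h interpolated between the 12-h and (24 + x)-h values. In units of dose/volume:

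C(t) = ka/(ka − ke) × [e^(−ke·t)/(1 − e^(−24ke)) − e^(−ka·t)/(1 − e^(−24ka))]

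The late sample has concentration C(x), because the next interval repeats the same profile.

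**Three worked cases.**

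| Half-life, ka | x | C(12) | True C(24) | Late sample | C(24) used | 12–24 h area, true → used | AUCtau, true → used | Ratio |
|---|---|---|---|---|---|---|---|---|
| 24 h, 1/h | 15 min | 1.456 | 1.030 | 1.243 | 1.247 | 14.77 → 16.19 | 34.55 → 35.97 | 1.041 |
| 12 h, 2/h | 15 min | 0.686 | 0.343 | 0.729 | 0.728 | 5.94 → 8.49 | 17.25 → 19.79 | 1.147 |
| 12 h, 2/h | 60 min | 0.686 | 0.343 | 1.157 | 1.120 | 5.94 → 10.84 | 17.25 → 22.15 | 1.284 |

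In the last row the segment should be a log-down trapezoid: 12 × (0.686 − 0.343)/ln(0.686/0.343) ≈ 5.94. It becomes a linear-up one: 12 × (0.686 + 1.120)/2 ≈ 10.84.

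**Range.** For 15–60 min after the tablet, AUCtau is inflated by 4.1% to 28.4% and the late concentration is 1.21 to 3.37 times the true trough. PTF% is multiplied by 1/1.284 = 0.78 to 1/1.041 = 0.96, since Cmax and Cmin do not change. At 10 min, which can still be in window, the inflation is about 3% to 11%. With half-life 8–36 h and ka 1–3 per h, the AUC ratio is 1.03 to 1.29 at 15 min and 1.07 to 1.46 at 60 min. The bias is upward throughout.

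**Geometric mean ratio (GMR).** With 16 participants in balanced sequences, one affected participant-period moves ln(GMR) by ln(ratio)/16:

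- ln(1.041)/16 = 0.0025, about 0.3%
- ln(1.284)/16 = 0.0156, about 1.6%

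Four participants at +20%, all in the same treatment, would give exp(4 × ln(1.2)/16) = 1.047, or 4.7%.

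**Other parameters.**

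- Cmin,ss: ratio 1.00 if only one of the two troughs is late, because the other supplies the minimum. It changes only if both are late.
- Day 14 pre-dose sample taken after the tablet: AUCtau rises by at most 1.2% (at most 1.9% in the wider range), because it affects only the first half-hour segment.

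**The case against.** The strongest reply is that the plan has safeguards. The event is a declared deviation, so the data review will see it. The PK Analysis Set definition (SAP 8.2) allows a participant to be excluded when the concentration-time profile is unreliable, and SAP 10.2.2 foresees excluding individual concentrations. This stands in part: distortion is possible, not automatic. But both routes are discretionary. SAP 10.2.2 gives no criteria, and SAP 8.2 removes the whole participant where one concentration is at fault.

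Second, exposure is small. Participants are in-patients from the evening of Day 13 until discharge on Day 15, and the 24-h window is tight. This also stands. However, Protocol 4.2 places the last sampling before the Day 15 cladribine/placebo dose and does not state the order relative to the Microgynon tablet, which Protocol 6.6.3 puts 1 hour before that dose.

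Third, Appendix 6 names no method for the concentration at tau, so interpolation towards the late sample is an assumption, and it drives the 4% to 28%. That is fair. Still, Appendix 6 corrects for time and does not tell the analyst to set the contaminated value aside.

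A reader might infer more than the documents support:

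- That Ctrough is misreported. Its definition requires a sample directly before the next administration, so a later sample already fails it; 16.1.4 merely lacks a step that enforces this.
- That Cmin,ss is generally wrong. It is taken over the whole interval and is protected unless both troughs are late.
- That a late Day 14 pre-dose sample matters for AUC. The effect is about 1–2% at most. Whether the time-zero rule covers such a sample is also debatable, since SAP 16.1 assigns time zero to pre-dose samples that precede the first administration.
- That keeping out-of-window samples is wrong in general. With actual times it is sound; only a draw after the next tablet is the problem.

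**Conclusion.** The point holds for one case. As written, the SAP bars a 24-h EE/LNG sample drawn after the Day 15 tablet from trough summaries, yet lets it determine the last segment of a primary endpoint. Under the assumed half-life and ka, the inflation of one profile's AUCtau,ss is about 4% to 28% for 15–60 min, and one affected participant among 16 moves the GMR by about 0.3% to 1.6%. The upward direction held throughout the range tested; the size depends on PK values that the documents do not give.

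It would be tempting to conclude that the bioequivalence decision is at risk or tilted towards no interaction. The documents do not support that. Both treatments are double-blind on the same schedule, nothing links late draws to one of them, and isolated shifts of this size are small against 0.80 to 1.25. This is a rule that is wrong as written for a foreseeable event, of low severity.

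**What to change.** Add to SAP 16.1.4: any 24-h EE/LNG sample drawn after the next Microgynon dose, judged by actual recorded times and whether or not it is in window, is excluded from the NCA and not reported as Ctrough. The concentration at tau is then estimated by log-linear extrapolation from the last valid samples of that profile, as an explicit exception to the rule against further imputation. If this is not possible, AUCtau,ss is set to missing. All other out-of-window samples stay in the NCA with their actual times. A cross-reference from SAP 8.1 would tie the two rules together.

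The drafting cost is a few sentences and no new data. There are two downsides. Extrapolation assumes that the decline seen up to 12 h continues to 24 h, and it would underestimate the concentration at tau if the later decline is slower. And a participant whose AUCtau,ss is missing leaves the PK Analysis Set, which requires all four primary endpoints, while Protocol 7.2 asks that 16 evaluable participants be maintained. Extrapolation should therefore come first and a missing value be the fallback.
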